7.5.5.5 Procedures to Prevent "Lost to Follow-up"

The Investigator must make every effort to contact subjects who fail to return for scheduled visits so that they will not be declared "lost to follow-up." These actions must include, but are not limited to, the following:

1. Contact all numbers for the subject and their listed contacts (to be collected in source at the subject's entry into the study), as applicable. This includes making calls after normal business hours or on holidays and weekends.
2. Contact the subject's primary care physician, referring specialist, pharmacist, and/or other healthcare professional (using the contacts provided by the subject at entry into the study), as applicable
3. Send email, text, and postal mail with registered (traceable or trackable) letters to all the subject's addresses and contact persons, as applicable. Registered (traceable or trackable) letters will be returned with a copy of the signature from whomever signed, which can be compared to the ICF for vital status data. If undeliverable, then send non-registered standard letters, which may be forwarded to a new address if the subject has moved.
4. Review available medical records/notes for details of hospitalizations, clinic visits, or other procedures that may indicate the status of the subject, as applicable.
5. Utilize the internet to search for additional contact information, as applicable.
6. Check local, regional, and national public records to locate the subject or search for mortality status as allowed by law, as applicable.

It is important to obtain at a minimum vital status (alive or deceased) at the global study completion for all randomized subjects, including those that have been LTFU during the course of the study.

The Sponsor may utilize a third-party provider in accordance with all applicable guidelines and legislation to assist the site in locating contact information for all subjects during the study or in locating the vital status for all of their randomized subjects in anticipation of global study completion (end of trial).

8 STUDY PRODUCT AND TREATMENT OF SUBJECTS

8.1 Study Product, Supplies, and Storage

Oral vadadustat and darbepoetin alfa for injection will be provided and shipped by the Sponsor or its designated supplier/distributor. Both vadadustat and darbepoetin alfa will be supplied as open-label supplies. All study medication supplies must be kept in a temperature-controlled, locked facility, accessible only to authorized study personnel.

The Investigator or designated study personnel will be responsible for preparing study medication for dispensing to the subject (Section 8.2, Dispensing Procedures) and for study medication supply accountability (Section 8.3, Product Accountability and Destruction).

8.1.1 Vadadustat

Vadadustat will be provided as 150 mg white to off-white, round, bi-convex film-coated tablets for oral administration. The tablets will be packaged in high-density polyethylene bottles with child-resistant closures, polypropylene liner, and induction seal. Labeling will be in accordance with current Good Manufacturing Practices (GMP) and local regulatory requirements.

Dose levels utilized in this study will include: 150 mg (1 tablet), 300 mg (2 tablets), 450 mg (3 tablets), and 600 mg (4 tablets) per day.

Vadadustat should be stored per the product label. Please consult the Pharmacy Manual for details on storage and managing temperature excursions.

8.1.2 Darbepoetin Alfa

Darbepoetin alfa will be provided in its commercially-approved primary packaging and stored per the PI for US sites or EU SmPC for non-US sites.

8.2 Dispensing Procedures

The Investigator will maintain record of all vadadustat tablets and darbepoetin alfa injections dispensed to and returned from each subject during the study. Subjects will receive either vadadustat tablets or darbepoetin alfa according to the randomization assignments provided via the IWR system (see Section 8.4.2, Randomization).

8.2.1 Dispensing of Vadadustat

Subjects will be provided with a supply of vadadustat at the Baseline visit according to the IWR system assignment. Resupply of additional vadadustat at subsequent visits will be managed via the IWR system and will be dependent on the current dose level of vadadustat and the number of tablets remaining in the subject's current vadadustat supply at a given study visit (Section 8.4.4.1, Vadadustat Dosing and Dose Adjustment Algorithms). Subjects will be instructed to finish 1 bottle before opening a new bottle.

At the Baseline visit, study subjects will be provided with 1 bottle of vadadustat. Each bottle of vadadustat will contain 100 tablets of vadadustat (150 mg tablets).

Subjects should be instructed to bring unused vadadustat and empty bottles to each study visit for product accountability. Empty bottles will be collected at these study visits. Previously dispensed bottles (whether opened or unopened) with remaining tablets may be redispensed to the subject during the dosing phase of the study.

A Vadadustat Dosing Information Sheet will be provided to the subject at dispensing of study medication.

8.2.2 Dispensing of Darbepoetin Alfa

Darbepoetin alfa will be dispensed according to the IWR system assignment. Dispensing of additional darbepoetin alfa at subsequent dosing visits will be managed by the IWR system (Section 8.4.4.2, Darbepoetin Alfa Dosing and Dose Adjustment Algorithms).

Darbepoetin alfa doses may be self-administered or staff-administered at the site facility or by the subject at home according to the Investigator's determination and local practice.

Subjects should be instructed to bring the darbepoetin boxes to each study visit for drug accountability. There will be no physical accountability performed with used syringes. The investigative site will maintain site drug accountability records of the actual syringes dispensed and used by a subject.

A Darbepoetin Alfa Dosing Information Sheet will be provided to the subject at dispensing of study medication.

8.3 Product Accountability and Destruction

Product accountability should be an ongoing process throughout the study. All study medication (vadadustat and darbepoetin alfa) must be accounted for and any discrepancies explained. The Investigator or designated study personnel are responsible for keeping accurate records of the clinical supplies received from the Sponsor, all supplies retained in inventory at the investigative site, and study medication dispensed to or returned from each subject. Records will be maintained that accurately reflect the drug accountability of vadadustat and darbepoetin alfa at all times.

Proper drug accountability includes, but is not limited to:

- Continuously monitoring expiration dates if expiry date or retest date is provided to the Investigator
- Frequently verifying that actual inventory matches documented inventory
- Verifying that the log is completed for all drug received and that all required fields are complete, accurate, and legible.

If any dispensing errors or discrepancies are discovered, the Sponsor must be notified immediately.

During the study, the Investigator will be notified of any expiry dates or retest date extensions of clinical study material. If an expiry date notification is received during the study, the investigative site must complete all instructions outlined in the notification, including segregation of expired clinical study material for return to the Sponsor or its designee for destruction.

Prior to investigative site closure and at appropriate intervals during the study, a representative from the Sponsor will perform clinical study material accountability and reconciliation.

At the end of the study, the Investigator will retain all original documentation regarding clinical study material accountability, return, and/or destruction, and copies will be sent to the Sponsor.

All unused and/or partially used vadadustat or darbepoetin alfa should be returned to the Sponsor or destroyed at the investigational site, as specified by the Sponsor. Appropriate records of the disposal will be documented and maintained. No unused vadadustat or darbepoetin alfa may be disposed of until fully accounted for by the Sponsor's monitor (or designee). Empty containers may be disposed of according to local procedures.

8.4 Treatment of Subjects

8.4.1 Treatment Group Assignments

Subjects will be randomized in a 1:1 ratio via the IWR system to either:

- Vadadustat (starting dose of 2 tablets once daily [300 mg/day])
- Darbepoetin alfa (starting dose based on the current PI for investigational sites in the US, and the SmPC for all other investigational sites (non-US), for adult patients with CKD not on dialysis).

For all subjects, it is recommended that no additional ESA doses be administered after SV2 and prior to the Randomization visit.

Target enrollment for each treatment group is approximately 925 subjects.

8.4.2 Randomization

This study will be open to approximately 1850 subjects with NDD-CKD with an eGFR ≤ 60 mL/min/1.73 m² (pre-dialysis).

Using an IWR system, eligible subjects will be assigned using permuted block randomization and a 1:1 ratio to either vadadustat or darbepoetin alfa during their Baseline visit.

To maintain balance between vadadustat-treated and darbepoetin alfa-treated subjects, randomization will be stratified with respect to: 1) geographic region (US vs EU vs ROW); 2) New York Heart Association CHF Class (0 (no CHF) or I vs II or III); and 3) study entry Hb level (< 9.5 vs ≥ 9.5 g/dL, based on the most recent central laboratory Hb measurement prior to the Baseline/Randomization visit).

8.4.3 Blinding

This will be an open-label study. Treatment assignment will be done through the IWR system and the Investigator, Sponsor, and CRO study teams will not be aware of which treatment will be assigned next. Treatments will be administered in an open-label fashion. The Sponsor and CRO study teams will be blinded to 'by treatment' aggregated analyses except for the unblinded statistician. In addition, the study will involve blinded adjudication of MACE, the use of an IDMC, and an identical schedule of visits, procedures, and assessments for both treatment groups in order to reduce the potential for bias. However, certain personnel directly involved in medical oversight of the study, regulatory reporting of safety information, and on-site monitoring activities may become unblinded to the treatment assignments of individual subjects during the course of the study.

The EAC will remain blinded throughout the full course of the study.

8.4.4 Dosing and Dose Adjustment Guidelines

Dosing will be initiated at the Baseline visit, and the first dose of study medication (vadadustat or darbepoetin alfa) will be administered at the investigative site after other Baseline visit procedures have been completed. The Investigator may elect to postpone the initial dose of study medication until a subsequent visit based on the subject's Hb level or Hb trajectory assessed at the Baseline visit.

Year 1-4 Treatment Period Visits

Hemoglobin will be monitored via HemoCue throughout the study to determine if the dose of study medication (vadadustat or darbepoetin alfa) will be adjusted, interrupted, or maintained. From Weeks 0 to 12, Hb will be obtained via HemoCue every 2 weeks for monitoring for dose adjustment. From Week 12 to Week 52, Hb will be monitored every 4 weeks via HemoCue.

From Week 53 through the study end, Hb will continue to be monitored via HemoCue to determine if the dose of study medication will be adjusted, interrupted, or maintained. Any unscheduled measurement between study visits will be recorded in the appropriate CRF and the subject's source when a HemoCue value is taken. Hemoglobin will also be assessed with a CBC through the central laboratory for efficacy and safety evaluations; however, dose adjustments should be based on the HemoCue Hb value. If the Investigator has an immediate clinical concern about a subject's HemoCue value, the Investigator may use clinical judgement and repeat the HemoCue Hb, use local lab values or wait for central lab results. The test method utilized to inform the treatment decision must be recorded in the appropriate CRF and the subject's source.

Year 2-4 Monthly Hb Monitoring

Additionally, after Week 52, the Hb drawn as part of the local standard of care labs must be monitored monthly for dosing oversight. Per the dosing algorithms, if the Hb value suggests a dose adjustment is needed, an unscheduled visit must be performed.

If monthly standard of care labs are not available, a study unscheduled visit must be performed. This visit will include, at minimum, the Hb measurement via HemoCue, dose adjustment assessment, and adverse events assessment.

The monthly Hb monitoring method is flexible between study visits after Week 52 to minimize unnecessary travel or redundant blood sampling for the subject.

The aim is to increase and maintain a Hb level of 10.0-11.0 g/dL in the US and 10.0-12.0 g/dL outside of the US throughout the study.

Dose adjustments for vadadustat and darbepoetin alfa will be guided by Hb concentration and the Dose Adjustment Algorithms. The Dose Adjustment Algorithm for darbepoetin alfa will follow the PI for investigational sites in the US, and the SmPC for all other investigational sites (non-US).

This protocol provides guidance for the treatment of subjects with anemia associated with CKD in order to achieve and maintain Hb levels within the target Hb range. Dose adjustment should be based on the Investigator's clinical discretion, incorporating the protocol guidance and considering the subject's clinical condition, Hb rate of rise, Hb rate of decline, Hb variability, and ESA responsiveness. In cases where the Investigator does not follow the dosing algorithm, the clinical circumstances must be documented in the subject's source.

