7.5.5.1 Temporary Interruption of Study Medication

Subjects who temporarily interrupt study medication (vadadustat or darbepoetin alfa) treatment after the first dose and prior to completion of the study will continue with study visits and assessments. Unless contraindicated, treatment should be resumed wherever possible and routinely considered at every visit following study medication discontinuation. If a subject does not return for a scheduled visit, every effort should be made to contact the subject. If a subject's study medication has been temporarily interrupted for more than 60 days, the Investigator should contact the Medical Monitor before resuming study medication.

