11 DATA ANALYSIS

Data collected throughout the study will be summarized using descriptive statistics and listed in by-subject listings. Continuous variables will be summarized using number of subjects with data, mean, standard deviation, median, minimum, and maximum. For categorical variables, the number and percentage of subjects in each category will be tabulated. Summaries will be provided by treatment group within appropriate analysis populations (as defined in [Section 11.2, Study Analysis Populations](#)) and by time point/time period as appropriate.

For Hb, Baseline will be calculated as the average of the central laboratory Hb measurements of samples taken at the screening visit closest to the date of randomization and the measurement taken at randomization.

For other parameters, unless otherwise specified, Baseline will be defined as the last available value prior to the first dose of study medication.

Hemoglobin values as assessed through the central laboratory will be used for efficacy and safety evaluations; local HemoCue Hb values will be used only for dose adjustments.

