11.2 Study Analysis Populations

The following analysis populations will be used in this study:

- Randomized population: defined as all randomized subjects
- Full analysis population: defined as randomized subjects receiving 1 or more doses of study medication and had at least one Hb assessment during the primary efficacy evaluation period. This population will be analyzed based upon the randomized treatment.

- Per protocol (PP) population: defined as all randomized subjects who received study medication (vadadustat or darbepoetin alfa) during the primary evaluation period, had at least 2 Hb assessments during the primary evaluation period, and received no rescue therapy (with ESA or RBC transfusion) in the 8 weeks prior to the evaluation period, and have no protocol deviations affecting the primary endpoint analyses. Protocol deviations leading to exclusion from the per protocol population will be specified prior to database lock on a blinded basis and recorded in a separate document.
- Safety population: defined as all subjects who received at least 1 dose of study medication. This population will be analyzed based upon the actual treatment received.

Efficacy analyses will utilize the randomized, full analysis, and PP populations while safety analyses (including MACE) will utilize the randomized population.

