11.7 Safety Analyses

All analyses of safety data will use the randomized population.

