11.7.2 Analysis of Adverse Events

Adverse events will be summarized using the number and percentage of subjects with AEs for all subjects in the safety population. Summaries will also be provided for subgroups including Region, Age, Gender and Race.

All AEs will be coded using MedDRA. Treatment-emergent and post-treatment AEs will be summarized by System Organ Class and Preferred Term for each treatment group. Adverse events will also be summarized by their maximum severity.

Summaries will also be provided for the following types of AEs:

- SAEs
- Related AEs (including all categories for relationship to study medication other than “Unrelated”, as determined by the Investigator)
- AEs leading to early discontinuation of study medication

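### The choice to defer the first dose is not required before open-label allocation, and the default non-Hb Baseline is tied to first dose rather than to randomization

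*Protocol*

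**What the plan says.** All references are to the current protocol (Amendment 7).

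- **First dose.** Section 8.4.4 says it "will be administered at the investigative site after other Baseline visit procedures have been completed". It then adds: "The Investigator may elect to postpone the initial dose of study medication until a subsequent visit". The stated basis is the Hb level or trajectory at the Baseline visit. The permission is repeated in the synopsis and in sections 8.4.4.1 (vadadustat) and 8.4.4.2 (darbepoetin alfa).
- **Allocation.** Sections 8.4.2 and 8.4.3 place IWR randomization at the Baseline visit and make treatment open-label. Section 9.3.4 lists randomization among the Baseline procedures, and lists a HemoCue reading for dose initiation under study medication procedures.
- **Limit on delay.** None is given. The nearest rule, in section 7.5.5.1, concerns "Subjects who temporarily interrupt study medication (vadadustat or darbepoetin alfa) treatment after the first dose and prior to completion of the study". It asks only for contact with the Medical Monitor once "study medication has been temporarily interrupted for more than 60 days".
- **Baseline.** Section 11 fixes Hb Baseline as the average of the central-laboratory value from the screening visit closest to randomization and the value at randomization. For other parameters, unless otherwise specified, "Baseline will be defined as the last available value prior to the first dose of study medication".
- **Safety analyses.** Section 11.2 says "safety analyses (including MACE) will utilize the randomized population", and section 11.7 says "All analyses of safety data will use the randomized population".

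**The concern.** In an open-label trial, a discretionary decision that can be taken before allocation should be. Start-or-defer is such a decision: the screening Hb values and the Baseline HemoCue reading can both be in hand before the IWR assigns an arm. As written, nothing stops the investigator from allocating first and deciding afterwards, so the start of treatment could differ by arm for reasons other than the subject's Hb. This sits awkwardly with section 6.2, which relies on the dosing algorithms to limit subjectivity in open-label dosing.

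A mechanism is conceivable. Table 1 reports that the US darbepoetin label advises reducing or interrupting the dose above 10 g/dL in patients not on dialysis. Eligibility rests on a mean screening Hb below 10.0 g/dL, so a Baseline-visit reading can be higher. That is a reason for care, not evidence of an effect.

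The Baseline definition adds to this. If first dose moves, non-Hb Baseline can move with it, so its timing depends on a choice that may be arm-aware. For iron indices, the moved value may also follow oral iron, which section 9.3.4 allows from the Baseline visit.

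At stake are early results such as time to an Hb rise above 1.0 g/dL (section 5.3) and the change-from-Baseline summaries of vital signs and laboratory values (section 11.7.3).

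**Working it through.** **1. The plan's own figures.** They reproduce, and this point changes none of them.
- MACE: 4 × (1.960 + 0.842)² / (ln 1.25)² rounds up to 631 events, as in section 11.1.2.
- Hb (SD 1.5, margin 0.75, 925 per arm, section 11.1.1): SE = 1.5 × √(2/925) = 0.0697. Then 0.75/0.0697 − 1.96 = 8.8, so power exceeds 99.9%, consistent with the stated >90%.

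**2. Order of steps.** Section 8.4.4 puts the first dose after the other Baseline procedures, and section 9.3.4 includes randomization among those. No section places the start-or-defer choice before allocation. Sections 8.4.4.1 and 8.4.4.2 repeat the permission for subjects whose arm is already assigned. An arm-aware choice is therefore permitted; it is not prescribed.

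**3. How far non-Hb Baseline can move.** The visit window at Weeks 2 to 12 is ±3 days (section 9). The schedule is in section 9.3.5. Samples are taken to be drawn before the deferred dose.
- Week 2 start: 14 ± 3 = 11 to 17 days after randomization. Vital signs and non-Hb CBC parameters are affected.
- Week 4 start: 28 ± 3 = 25 to 31 days. This adds eGFR, liver tests, iron indices, reticulocytes and EPO.
- Never dosed: the reference date does not exist, yet section 11.7 keeps these subjects in the safety analyses.

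**4. The 60-day rule as a cap.** It starts after first dose, so it does not apply to postponement. Even read across, 60/7 = 8.6 weeks. The Week 8 visit falls at day 56 ± 3 = 53 to 59, so the Week 2, 4, 6 and 8 visits would all pass before contact was asked for.

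**5. Time to Hb response (assumed inputs).** Assume a between-arm difference in postponed share of 2 to 10 percentage points, a delay of 2 to 4 weeks, each postponed response delayed by the full postponement, and time counted from randomization.
- Low: 0.02 × 2 = 0.04 weeks = 0.3 days.
- High: 0.10 × 4 = 0.40 weeks = 2.8 days.

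**6. Primary endpoint (assumed inputs).** A 10-point difference with a 0.5 g/dL deficit still present at Weeks 24 to 36 gives 0.10 × 0.5 = 0.05 g/dL. The margin is 0.75 g/dL, and the unadjusted 95% CI half-width is 1.96 × 0.0697 = 0.137 g/dL. With 20% of one arm postponed the shift is 0.20 × 0.5 = 0.10 g/dL, and power stays above 99.9%.

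**The case against.** The strongest reply has four parts.

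1. **The Baseline default is qualified.** Section 11 says unless otherwise specified, and section 11.7.3 leaves detail to the SAP. This stands as a limit: the SAP may already override the default. The protocol's stated default is still the wrong one for a design that permits a post-randomization start.
2. **Arm-awareness is inferred from silence.** The permission is the same in both arms, has a clinical basis, and section 8.4.4 requires the test method behind a treatment decision to be recorded. It is true that the order of steps is not stated. But recording the test method does not show that the choice preceded allocation.
3. **Arm-aware discretion continues after Day 1 anyway.** Interruption, departure from the algorithm and discretionary ESA rescue all remain. This stands: the fix removes one avoidable opening, not all of them.
4. **The effect is small.** This stands in full.

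A reader might go further and infer any of the following. The document does not support them.
- *That non-Hb Baseline could be a post-dose value.* It is by definition before first dose, so it is free of study drug.
- *That Hb Baseline moves too.* Section 11.5 speaks loosely of the pretreatment period, but section 11 fixes Hb Baseline at screening and randomization.
- *That noninferiority or MACE is compromised.* The primary analysis uses the randomized population as assigned (section 11.6.1.1), MACE time starts at randomization (section 11.1.2), and AE collection starts there too (section 10.3.1).
- *That never-started subjects drop out of the AE tables.* Section 11.7.2 says "Adverse events will be summarized using the number and percentage of subjects with AEs for all subjects in the safety population", which conflicts with sections 11.2 and 11.7. That conflict exists regardless of postponement and is not settled here.
- *That the Day 1 dosing wording in sections 9.2.2, 9.3.2 and 9.3.4 is a separate contradiction.* It is a missing cross-reference.

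**Conclusion.** The point holds in a limited form. The investigator may defer the first dose after learning the arm, with no latest start visit, and the default non-Hb Baseline can then fall after randomization or, for a subject never dosed, not exist. The consequences are confined to early secondary results and descriptive safety summaries. A shift of 0.3 to 2.8 days in mean time to response, and about 0.05 g/dL on the primary endpoint, rests wholly on assumed postponement differences and delays. The Baseline shifts of 11 to 17 and 25 to 31 days follow from the visit schedule itself.

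No Hb threshold for starting is criticized, because the algorithm figures are not shown. The change is worth making because it costs almost nothing, not because a main conclusion is at risk.

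**What to change.** - **Section 9.3.4.** Take the existing HemoCue reading, record start-or-defer in the IWR, and only then allocate. A subject marked as deferred is still randomized at that visit.
- **Synopsis and sections 8.4.4, 8.4.4.1 and 8.4.4.2.** Keep the permission to defer for safety, state that the choice precedes allocation, and name a latest start visit. Cross-refer to this from the sections that assume a Day 1 dose.
- **Section 11.** Define non-Hb Baseline as the last value on or before the randomization visit, including that visit's pre-dose samples. This also covers subjects who are never dosed.

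Do not withhold randomization from deferred subjects. That would turn a local HemoCue reading into an entry gate, although eligibility rests on central-laboratory Hb (sections 7.2 and 7.4.1). It would also push some candidates past the 8-week screening window into rescreening, with new consent and all procedures repeated, within the limit of 3 attempts (section 7.4.2).

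The cost is a small reordering of Baseline steps with a decision entry in the IWR. For late starters, Baseline sits somewhat further from first dose: up to 31 days for a Week 4 start. No test is added and enrollment is unchanged.
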